1.0 Study Summary

Study Title	Validation and application of wearable sensors for capturing responses to losses of balance
Study Design	A three-group posttest-only design.
Primary Objective	To validate the use of wearable sensors for capturing responses to losses of balance (LOBs). During laboratory testing, we will use both wearable sensors and a laboratory-based optoelectronic motion capture system to measure responses to LOBs after laboratory-induced trips and slips. During real-world testing, we will use wearable sensors to measure responses to LOBs after any naturally-occurring trips or slips during the real-world daily lives of participants. Participants for this primary objective are referred to as "non-balance training participants."
Secondary Objective(s)	Responses to LOB measured during both laboratory testing and real-world testing will be used to compare between three types of balance training. Participants for this secondary objective are referred to as "balance training participants."
Study Population	Adults age 65-80
Sample Size	60 total including 30 non-balance training participants and 30 balance training participants.
Research Intervention(s)/Investigational Agent(s)	Data will be obtained using 1) a laboratory-based optoelectronic motion capture system to measure responses to LOBs (i.e. body movements) after laboratory-induced trips and slips, 2) wearable sensors to measure responses to LOBs after laboratory-induced and any naturally-occurring real-world trips and slips, 3) a wearable voice recorder to describe any real-world trips or slips. For balance training participants, each participants will complete one of three different research interventions: non-treadmill training (NT); treadmill training (TT); or strength training (ST). All interventions will be performed two times per week for three weeks. In this document, balance training participants will be referred to as NT participants, TT participants, or ST participants (depending upon which intervention they complete).
Study Duration for Individual Participants	The study duration for individual participants will be 5-7 weeks, not including screening.
Acronyms and Definitions	LOB - Loss of balance PBT - perturbation balance training NT - Non-treadmill training TT - Treadmill training ST - Strength and balance training

2.0 Objectives

2.1 Describe the purpose, specific aims, or objectives of this study:

The primary objective is to validate the use of wearable sensors for capturing responses to losses of balance (LOBs). During laboratory testing, we will use wearable sensors and a laboratory-based optoelectronic motion capture system to simultaneously measure responses to LOBs after laboratory-induced trips and slips. During real-world testing, we will use wearable sensors to measure responses to LOBs after any naturally-occurring trips or slips during the real-world daily lives of participants.

The secondary objective of this study is to compare the effects of three balance training exercises on responses to LOBs measured in the laboratory and in the real-world during daily life.

2.2 State the hypotheses to be tested:

Hypotheses for our primary objective that will involve non-balance training participants:

Hypothesis 1: LOB response measures obtained from the wearable sensors after lab-induced trips and slips will exhibit statistical agreement with the same measures obtained simultaneously from a laboratory-based optoelectronic motion capture system.

Hypothesis 2: Real-world LOB responses will show greater variety than laboratory-induced LOB responses.

Hypotheses for our secondary objective that will involve balance training participants:

Hypothesis 3: NT and TT participants will exhibit improved LOB responses after lab-induced trips and slips compared to ST participants.

Hypothesis 4: NT and TT participants will exhibit statistically-equivalent LOB responses after lab-induced trips and slips.

Hypothesis 5: NT and TT participants will exhibit improved LOB responses after any naturally-occurring real-world trips and slips.

3.0 Background

3.1 Summarize the relevant prior research on this topic and gaps in current knowledge within the field of study:

21-1072 Validation and application of wearable sensors for capturing responses to losses of balance

Falls are the leading cause of injuries among older adults. An estimated 60% of falls among community-dwelling older adults are due to LOBs induced by tripping or slipping [Berg 1997]. Laboratory studies have shown that these falls generally result from an age-related decline in balance recovery ability after an LOB [Pavel 2007; van Dieen 2005]. However, technical challenges with capturing the kinematics of these events outside the lab has resulted in at least two knowledge gaps that limit progress in fall prevention research. First, there is a need to validate the use of wearable sensors (that can be used outside the lab in the real-world) by comparing their measurements with a gold-standard laboratory system. Second, it is unclear if gait and tripping/slipping events differ meaningfully between the laboratory and real-world. Laboratory trips and slips are contrived, highly-controlled, and often not unexpected, and likely result in more stereotypical LOB responses. Real-world trips and slips are typically unexpected, have more variable etiology and environmental contributions, and as a result likely elicit more variable LOB responses. Accordingly, there is a critical need to evaluate the use of wearable sensors to capture responses to LOBs both in the laboratory and in the real-world.

Multiple studies report a reduction in real-world fall risk after perturbation-balance training (PBT) [Rosenblatt 2013; Grabiner 2012; Bhatt 2012]. These studies speculate that this reduction in fall risk is due to improved responses to LOBs. An LOB is defined as an event when the postural control of the body that resists gravity (balance) is momentarily lost, and is then followed by either successful recovery of balance without a fall, or a fall. To our knowledge, no studies have shown a direct training effect of PBT on responses to real-world LOBs. Until a real-world effect is demonstrated, PBT studies reporting a reduction in falls may be confounded by concomitant changes such as in activity intensity, safe/risky behavior, and the daily living environment rather than true PBT-induced improvements in balance.

Preliminary data on PBT from our group is cited below. In short, these data show PBT improved LOB responses after lab-induced trips and slips.

In Bieryla et al. (2007), we showed beneficial effects of TT on laboratory-induced trips. In Allin et al. (2019), we showed beneficial effects of slip training on laboratory-induced slips. In Allin et al. (2020), we showed beneficial effects of TT on laboratory-induced trips and slips.

Bieryla KA, [name] ML, Nussbaum MA. Practicing recovery from a simulated trip improves recovery kinematics after an actual trip. *Gait & Posture*, 2007, 26(2), 208-213.

21-1072 Validation and application of wearable sensors for capturing responses to losses of balance

3.3 *Based on the existing literature, provide the scientific or scholarly rationale for and significance of your research and how will it add to existing knowledge:*

This study will address two major knowledge gaps in the literature.

First, there is a need to validate the use of wearable sensors (that can be used to capture responses to LOBs in the real-world) to measure responses to LOBs with simultaneous measures obtained from gold-standard laboratory-based equipment.

Second, PBT studies aiming to reduce the risk falls have almost exclusively used specialized treadmills to apply perturbations during training. While this type of training has shown beneficial effects on responses to laboratory-induced LOBs, the cost of these specialized treadmills may present a barrier to widespread adoption of this training by some individuals or organizations. This study will evaluate an alternative PBT not requiring a specialized treadmill that would alleviate cost as a barrier to its use, and measure the effects of this training on responses to LOBs after both laboratory-induced trips and slips, and naturally-occurring trips and slips.

4.0 Study Endpoints

4.1 *Describe the primary and secondary **study** endpoints. See links below for discussion of study endpoints and how they may differ from study objectives. These are most common in clinical trials but are sometimes applicable to other types of biomedical research, as well as social, behavioral, or educational research. See link below for a discussion.*

https://docs.google.com/document/d/1Wocz7K7a0hCQJPO_khh511SOQjhGDDGHzcOPRHR5Tw/edit?usp=sharing

Study endpoints for all participants will include:

- 1) measurements of body movements during responses to LOBs after lab-induced trips and slips
- 2) two or three weeks of using wearable sensors to measure body movements during responses to LOBs after naturally-occurring trips and slips during daily life
- 3) during the two or three weeks of using wearable sensors, participants will also use a digital voice recorder to record a description of the context of each real-world LOB. Specifically, participants will be asked to make a short recording

21-1072 Validation and application of wearable sensors for capturing responses to losses of balance

after each LOB to describe (1) what they were doing at the time (e.g., “I was walking across my living room”), (2) how they lost their balance (e.g., “I tripped over my dog”), (3) why they lost their balance (e.g., “my dog ran in front of me to bark at the mailman”), and (4) the results of LOB (e.g., “I fell, or did not fall, as a result”).

4.2 *Describe any primary or secondary safety endpoints. These should be included for all studies that are greater than minimal risk. (Minimal risk: The probability and magnitude of harm or discomfort anticipated in the research that are not greater in and of themselves than those ordinarily encountered in daily life or during the performance of routine physical or psychological examinations or tests.):*

No safety endpoint is included while using wearable sensors in the real-world during daily life because the use of the wearable sensors does not increase risk above that normally experienced during every day life.

During balance training (among balance training participants), safety endpoints will include number of times the spotter is needed to provide support to the participant during training, and the number of times the participant is fully supported by the harness during measurements of responses to lab-induced LOBs.

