To address our secondary objective, balance training participants will be assigned to one of three balance training exercises/interventions including TT, NT, and ST. No drugs are used in this study. Each training session for TT, NT, and ST will be one-on-one with the investigator, approximately 30-45 minutes in duration, and two sessions will be completed each week for three weeks. A description of each session of each type of training follows.

Each TT session will involve a trip training protocol with a specialized treadmill (Aviles et al., 2019). TT perturbations will be induced while participants are standing on a modified treadmill (Freemotion 800, Freemotion Fitness, Logan, UT). The treadmill belt will then be accelerated posteriorly, varying in speed from 0.5 to 2.4 mph, to induce a forward LOB within about 40 msec. Participants will be instructed to react naturally and try to establish a stable gait after perturbations and an initial step over an obstacle. The treadmill belt speed will be maintained until one of two conditions are met: (1) participant established a stable gait for several strides, or (2) participant received substantial support from a fall protection harness or spotter(s) standing next to him/her. Based upon the performance of participants, the treadmill speed will progressively be increased during each session to continue challenge participants and to maintain variability over the course of training. Perturbations in the reverse belt direction (i.e., 0.5 mph anteriorly) will also be included intermittently to reduce anticipation. A slender, lightweight rectangular foam block (7.5 cm x 7.5 cm cross section) will be placed within 3-7 cm in front of the toes before each trial to elicit a step over an obstacle, similar to that needed during an actual trip. Given the suddenness of these perturbations, participants will wear a fall protection harness supported by an overhead gantry to protect knee or hand from contact with the treadmill in the event of an unsuccessful attempt to recover balance. Each TT session will involve exposure to up to 40 treadmill perturbations with a rest break after every 10 perturbations.

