Each NT session will involve four phases of voluntary/volitional stepping exercises. Each session will begin with a three-minute warm-up of walking on a treadmill and light stretching. Phase 1 – Rapid Stepping will involve volitional stepping exercises from bilateral standing where a participant will start to fall forward and then take quick steps to recover balance. This exercise will be performed first without tripping obstacle, and then with a slender, lightweight rectangular foam block (7.5 cm x 7.5 cm cross section) placed in front of the toes before stepping. Phase 2 – Trunk Control will involve similar stepping exercises as Phase 1, but with explicit instructions and emphasis on arresting trunk motion and controlling trunk posture to be vertical at touchdown of the first recovery step. Phase 3 – Lean Release will involve similar exercises as Phases 1 and 2, but with the addition of an “unexpected” forward LOB. The participant will lean slightly forward while being supported by a trainer with their hands on the participant’s shoulders and arms fully extended in front of the participant. Without warning, the trainer will release the participant, and the participant will take recovery steps to recover balance. Phase 4 – Simulated Trip will self-induce a slow-motion trip and practice stepping over the obstacle and continue walking. The participant will stand 15-30 cm away from the tripping obstacle, swing their foot forward to purposefully trip on the obstacle, then elevate the

21-1072 Validation and application of wearable sensors for capturing responses to losses of balance

obstructed foot over the obstacle to recover balance, and continue walking. We will encourage participants to take a long initial recovery step and control trunk posture to be vertical at touchdown of the first recovery step. To prevent a fall in the event of an unsuccessful balance recovery during any of the four phases of NT, the investigator and spotter will be nearby to provide support if needed. The investigator will also demonstrate each phase before asking the participant to complete them, and if necessary assistance will be provided during initial attempts by the participant. Each NT session will be individualized to each participant's capability and rate of improvement to continuously challenge the participant while not asking them to overexert themselves.

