21-1072 Validation and application of wearable sensors for capturing responses to losses of balance

weights and using more challenging balance postures. The progression of difficulty will be based on the investigators perception of the improving ability of the participant.

- If the participant is assigned no training, then no such training will be performed.
- All participants will then complete the two types of LOB response measurements described below.

Measure LOB responses in the laboratory:

- Each participant will complete a lab session to assess their response to an LOB after lab-induced trips and slips. This session will take place in our research lab on the VT campus ([name]). During these sessions, participants will wear a safety harness supported overhead to prevent impact with the floor in the event of an unsuccessful balance recovery. First, the appropriate size will be selected from a range of sizes we have in the lab. Second, the investigator will assist the participant in donning the harness, securing all straps and connections, and inspecting and confirming the overall fit. The PI ([name]) has extensive experience with the harnesses, and will train the student investigators in their use.
- Participants will also wear reflective markers so researchers can measure their movements with a laboratory motion capture system. As we have done for years, these markers will be affixed to clothing and skin at selected anatomical landmarks using double-sided tape. [name] will place markers on participants. Markers will be placed bilaterally on the shoes at the toes and heels, ankles, knees, hips, shoulders, elbows, wrists, and on a headband worn around the head.

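### The training safety count in section 4.2 does not record the same event in every arm, and it is unclear whether the lab harness count covers the 30 untrained participants

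*Combined protocol and SAP*

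**What the plan says.** Section 4.2 of the combined protocol and SAP has one sentence that defines safety endpoints. Its lead-in is "During balance training (among balance training participants), safety endpoints will include", and two counts follow. The first concerns training: "safety endpoints will include number of times the spotter is needed to provide support to the participant during training". The second is "the number of times the participant is fully supported by the harness during measurements of responses to lab-induced LOBs". The only phase that 4.2 excludes with a reason is home sensor wear: "No safety endpoint is included while using wearable sensors in the real-world during daily life".

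Section 7.1 describes how participants are protected in training. In TT, "participants will wear a fall protection harness supported by an overhead gantry", and one of the two conditions that end a perturbation is that the "participant received substantial support from a fall protection harness or spotter(s) standing next to him/her". For NT no harness is described; instead, "the investigator and spotter will be nearby to provide support if needed". Section 8.3(g) places an investigator and a spotter near participants in balance training generally, which takes in the strength arm (ST).

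For the lab session, section 8.2 says: "Each participant will complete a lab session to assess their response to an LOB after lab-induced trips and slips". It puts participants in an overhead harness for that session. Section 14.4 says that testing is the same for everyone apart from the training received.

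**The concern.** A safety count by arm is informative only if the same event is counted in each arm. Here the event of interest is a recovery that failed, so that someone or something had to take the participant's weight. Section 4.2 counts it only when the spotter was the source of support. The possible sources differ by arm, so two identical failures can be recorded differently depending on who or what made the catch.

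This matters because section 3.3 presents NT as an alternative that avoids the cost of specialized treadmills, and Hypothesis 4 looks for equivalence of NT and TT in the lab. A reader choosing between them will look at how often each needed a rescue in training. Section 21.1 places the safety concerns in the experimental and training sessions but names no data item, count, reviewer or trigger. The two counts in 4.2 are thus the only safety measures the plan specifies, and their scope should be clear.

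The second issue is scope by group. All participants are tripped and slipped in a harness, but the lead-in in 4.2 names only those who train. The untrained group is the natural reference for how often the harness is needed without training.

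**Working it through.** The plan gives no figure for these counts, so there is none to reproduce. The check sets the sources of support against the counts listed.

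**Sources of support and what 4.2 lists**

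| Setting | Possible source of support | Where stated | Listed in 4.2? |
|---|---|---|---|
| TT training | Spotter | 7.1 | Yes |
| TT training | Harness only | 7.1 | No |
| NT training | Spotter | 7.1 | Yes |
| NT training | Investigator | 7.1 | No |
| ST training | Spotter | 8.3(g) | Yes |
| ST training | Investigator | 8.3(g) | No |
| Lab session, 30 trained | Harness | 8.2 | Yes |
| Lab session, 30 untrained | Harness | 8.2, 14.4 | Unclear |

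A TT catch in which a spotter also helps is listed; a catch by the harness alone is not. TT is the only arm for which a training harness is described, so that gap is specific to TT. The investigator gap affects NT and ST if investigator and spotter are read as different people, as 7.1 and 8.3(g) name them.

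**Exposure in TT** (7.1 for sessions and perturbations; 14.4 for group size)

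- Sessions per participant: 2 per week × 3 weeks = 6.
- Perturbations per participant: at most 6 × 40 = 240.
- Across the arm: at most 240 × 10 = 2,400.

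These are ceilings on exposure, because 40 is a maximum per session and the total includes the intermittent low-speed perturbations in the reverse direction. The documents give no catch rate, so the number of harness-only catches cannot be estimated. Section 7.1 gives no repetition count for NT or ST, so a rate per attempt cannot be formed in those arms unless attempts are recorded.

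**Lab session**

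- Participants in the session: 30 + 30 = 60.
- Participants whose coverage is unclear: 30/60 = 50%.

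**Reading the lead-in.** Taken literally, it limits both counts to the period of training and to balance training participants. The second count cannot meet the first limit, because the lab session follows training (5.1, 8.1). Either the lead-in governs only the first count, and the harness count is for everyone, or the group limit carries over and the harness count is for the trained 30. The text does not settle which.

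**The case against.** Several points on the other side are sound.

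- **The list is open.** Section 4.2 says what the endpoints will include, which need not be exhaustive. Lab motion capture covers all participants, and section 8.4 provides for video during perturbations, so lab harness catches could be recovered later. This stands: the events are unspecified as endpoints, not lost. It does not close the training gap, because 8.4 specifies no count from the video and does not say whether training sessions are recorded.
- **No between-arm safety comparison is planned.** Section 5.2 has none, and belt perturbations differ in kind from mostly volitional stepping. This stands, and it limits the consequence to descriptive reporting.
- **A catch is not an injury.** The harms in section 17.1 are strains, soft-tissue injury, broken bones and overexertion. A catch is a near-miss marker. This also stands, but the plan itself chose support counts as its safety endpoints.
- **The lab count may be meant for everyone.** Sections 8.3 and 17.2 pair the spotter with training and the harness with testing, with no group limit on testing, and 14.4 says that testing is the same for all. This is a fair reading.

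A reader might infer three stronger things, none of which the documents support. First, that treadmill training will look safer by construction: investigator catches in NT are unlisted too, TT catches involving a spotter are counted, and neither shortfall can be sized. Second, that half the participants have no lab safety endpoint: that follows only from the stricter of two readings. Third, that up to 2,400 events are missed: that is a ceiling on perturbations delivered, of which harness-only catches are an unknown subset.

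**Conclusion.** The concern holds as a problem of definition. As written, the training safety count omits harness-only catches in TT and, where investigator and spotter are distinct, investigator catches in NT and ST. It therefore does not measure one event across arms. The direction and size of the resulting difference are not established. All that can be said is that TT alone has described harness catches, against an exposure of at most 240 perturbations per participant. The TT gap does not depend on how the lead-in of 4.2 is read.

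Whether the lab harness count covers the 30 untrained participants is an ambiguity, not a demonstrated exclusion. Nothing here touches the hypotheses, the sample size or any error rate. The change is worth making because it is cheap and these are the only safety counts specified.

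**What to change.** Reword section 4.2 so that it agrees with 7.1, 8.2 and 14.4:

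1. **Training, every arm.** Tally each instance of support by harness, spotter or investigator, with the source recorded. Report the number of perturbations or attempts alongside wherever it is recorded.
2. **Lab session, all 60 participants.** Count full harness supports per induced trip and per induced slip.
3. **Reporting.** Present both descriptively by group, with no test. State that training counts come from different kinds of exercise, so differences between arms are not directly comparable.

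The cost is the wording change, a tally sheet and a little extra recording. In TT the event is already observed because it ends the perturbation, and lab events can be read from the video and motion capture. No staff, visits or procedures are added, and no training or safety procedure changes.
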